Overview of the Approach: A total of 90 subjects (70 subjects with chronic HIV-1 infection and 20 HIVnegative control subjects) will be recruited (See Figure 2). For the neurological substudy, an additional 15 HIV-negative control subjects will be recruited and complete Visit A and Visit B (see Figure 1b, not shown in Figure 2 flowchart). Ninety subjects will complete **Baseline Study Part 1** of the cross-sectional study. **Baseline Study Part 2** will be performed in a subset of 60 HIV-infected patients and 10 HIVnegative controls. The 60 HIV-positive patients who complete Baseline Studies Part 1 and Part 2 will enter the **Randomized Study of Teduglutide vs. Placebo**. The tests and procedures obtained during the Baseline Studies Part 1 and Part 2 for these 60 HIV-positive participants will serve as the baseline measurements for the randomized study (they are not repeated) in order to minimize risk from exposure to study procedures for the participants and to maximally utilize the study data.

Having the control group will help us establish whether assessed relationships between GI epithelial integrity, microbial translocation, immune activation, and cardiovascular imaging markers are HIV-specific. Adding the neurological substudy control group (n=15) will help us potentially identify a HIV-

specific, cardiovascular and inflammatory link to cognitive impairment and depression. The control group can also serve as a comparison group with which to compare the HIV patients.

Figure 2

After all subjects have completed the study, transcriptomic profiling by RNA-Seq will be performed in 7 HIV+ participants with greatest degree of coronary disease seen on CTA vs. 7 HIV+ participants without and 7 HIV+ participants with the greatest degree of bacterial translocation vs. 7 HIV+ participants with the least amount of microbial translocation.

Participants will be recruited from the Boston area from infectious disease clinics, HIV community centers and also via IRB-approved advertisements. Patients will also be recruited via referral by primary care providers, infectious disease providers, newspaper advertisement, posted flyers, and Partners subject recruitment broadcast. After obtaining informed consent, baseline measurements and studies will be performed.

Inclusion criteria for HIV-infected participants:

- 1. Men and women age 21-65 with previously diagnosed HIV disease

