- 13. Subject taking any of the following medications: systemic steroids (inhaled or nasal steroid therapy is permitted), interleukins, systemic interferons (e.g. local injection of interferon alpha for treatment of HPV is permitted), systemic chemotherapy including oral chemotherapeutic agents, methotrexate, octreotide, growth hormone, antiarrhythmics including digoxin, antiepileptics, immunosuppressants, vancomycin, rifampin, aminoglycosides, clonidine, prazosin, lithium and ritonavir-boosted lopinavir (Kaletra).
- 14. Subjects receiving high dose statin therapy (a stable low or moderate dose of statin is permitted)
- 15. Initiation of statin therapy or change in statin dose <90 days prior to entry
- 16. Subject has had two or more of the same endoscopy procedures (sigmoidoscopy, or colonoscopy) within the past 12 months for clinical purposes or other research studies.
- 17. Body weight greater than 350 lbs
- 18. Active illicit drug use
- 19. Patients who report any significant radiation exposure over the course of the year prior to randomization. Significant exposure is defined as:
 - a) More than 2 percutaneous coronary interventions (PCI) within 12 months of randomization
 - b) More than 2 myocardial perfusion studies within the past 12 months
 - c) More than 2 CT angiograms within the past 12 months
 - d) Any subjects with history of radiation therapy
- 20. Patients already scheduled or being considered for a procedure or treatment
 - a) requiring significant radiation exposure (e.g., radiation therapy, PCI, or catheter
 - b) ablation of arrhythmia) within 12 months of randomization
- 21. History of malignancy in the last 5 years, with the exception of surgically cured non-metastatic

non-melanoma skin cancers

22. Prior recipient of a HIV vaccine

Inclusion/Exclusion Criteria for HIV-negative Controls

For the HIV-negative control group in the parent study and the neurological substudy, we will recruit a total of 35 men and women without known HIV disease with the same inclusion and exclusion criteria other than the inclusion criteria of presence of HIV infection and stable antiretroviral therapy.

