The Baseline Study Part 1 includes 10 patients with HIV and 10 patients without HIV and does not involve a colonoscopy, CT scan, or PET scan. Some of the exclusion criteria listed above are only relevant for participants undergoing a colonoscopy, CT scan, or PET scan. Patients participating only in the Baseline Study Part 1 will be excluded based on the following criteria only:

- 1. History of clinically significant gastrointestinal disease including but not limited to: colon cancer, intestinal obstruction, ulcerative colitis, Crohn's disease, or history of C. difficile within the past 3 months
- 2. First-degree relative with history of colon cancer
- 3. Active gall bladder, biliary or pancreatic disease
- 4. Female subject who is pregnant, nursing or less than 8 weeks post partum.
- 5. Use of any immunomodulatory agents within 30 days prior to study enrollment
- 6. Renal disease or creatinine >1.5 mg/dL (contrast will be administered during CT angiography of the heart)
- 7. History of myocardial infarction, decompensated cirrhosis, or any other condition that in the opinion of the investigator will compromise ability to participate in the study
- 8. Currently taking anticoagulants including but not limited to: heparin (Hep-Lock, Hep-Pak), Hep-Pak CVC, Heparin Lock Flush), warfarin (Coumadin), tinzaparin (Innohep), enoxaparin (Lovenox), danaparoid (Orgaran), dalteparin (Fragmin), clopidogrel (Plavix)
- 9. Subject taking any of the following medications: systemic steroids (inhaled or nasal steroid therapy is permitted), interleukins, systemic interferons (e.g. local injection of interferon alpha for treatment of HPV is permitted), systemic chemotherapy including oral chemotherapeutic agents, methotrexate, octreotide, growth hormone, antiarrhythmics including digoxin, antiepileptics, immunosuppressants, vancomycin, rifampin, aminoglycosides, clonidine, prazosin, lithium and ritonavir-boosted lopinavir (Kaletra).
- 10. Subjects receiving high dose statin therapy (a stable low or moderate dose of statin is permitted)
- 11. Initiation of statin therapy or change in statin dose <90 days prior to entry
- 12. Body weight greater than 350 lbs
- 13. Active illicit drug use
- 14. History of malignancy in the last 5 years, with the exception of surgically cured non-metastatic non-melanoma skin cancers

- 15. Prior recipient of a HIV vaccine
- 16. Currently receiving pre-exposure prophylaxis (PrEP)

IV. Subject Enrollment

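### The PrEP exclusion is listed only for Part 1-only participants, so the 25 HIV-negative controls who are imaged are not covered by it (minor)

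*Combined protocol and SAP*

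**What the plan says.** All references are to the combined protocol and SAP.

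- **Size of the control group** (section III, Overview of the Approach). The parent study is described as "A total of 90 subjects (70 subjects with chronic HIV-1 infection and 20 HIVnegative control subjects) will be recruited". For the neurological substudy, "an additional 15 HIV-negative control subjects will be recruited and complete Visit A and Visit B". Baseline Study Part 2 "will be performed in a subset of 60 HIV-infected patients and 10 HIVnegative controls".
- **Criteria for controls** (section III, Inclusion/Exclusion Criteria for HIV-negative Controls). The protocol says "we will recruit a total of 35 men and women without known HIV disease with the same inclusion and exclusion criteria", and the only departure it allows is "other than the inclusion criteria of presence of HIV infection and stable antiretroviral therapy". Controls thus take over exclusions 1 to 22, and no exclusion is added for them.
- **Criteria for Part 1-only participants** (same section, next paragraph). Ten people with HIV and ten without have Part 1 only. They get a separate list of 16 exclusions, introduced as shorter because some main criteria matter only for colonoscopy, CT or PET. Item 16 is "Currently receiving pre-exposure prophylaxis (PrEP".
- **Purpose of the controls** (Overview of the Approach). The text begins "Having the control group will help us establish whether assessed relationships between GI epithelial integrity" and goes on to ask whether those relationships, and those with immune activation and cardiovascular imaging, are specific to HIV. The neurological controls are added to look for an HIV-specific link to cognitive impairment and depression.

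**The concern.** HIV-negative controls are defined in two ways. For the 10 with Part 1 only, current PrEP disqualifies. For the other 25 it does not. The looser definition falls on the controls who supply all of the control colonoscopy, CTA and FDG-PET data, and on the whole neurological control group.

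Two things are at stake. First, controls taking antiretroviral drugs for prevention would differ from the remaining controls in a drug exposure that they share, at least in kind, with the treated HIV group. That could complicate any statement that a finding is specific to HIV. Second, I-FABP, LPS and sCD14 are to be measured in all 20 parent-study controls, and the SAP sizes a correlation within those 20. Half of them would have been screened for PrEP and half not.

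**Working it through.** **1. Head count.**

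Inputs: 20 parent-study controls, 15 neurological controls and 10 controls in Part 2 (Overview of the Approach); stated total 35 (criteria for HIV-negative controls); 10 Part 1-only controls (paragraph introducing the short list).

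- Total: 20 + 15 = 35, which reproduces the stated figure.
- Part 1-only: 20 − 10 = 10, which agrees with the stated figure.
- Not covered by the PrEP item: 35 − 10 = 25; cross-check 10 + 15 = 25.
- Shares: 25/35 = 71.4% not covered; 10/35 = 28.6% covered.

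**2. Which of the 25 are imaged.** Part 2 consists of colonoscopy, cardiac CTA and FDG-PET/CT. The neurological controls have cardiac CTA at Visit A and FDG-PET/CT at Visit B (section V; the Remuneration paragraph says the same). So 25 controls are scheduled for imaging, 10 of them also have colonoscopy, and none of the 25 is under the PrEP exclusion.

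**3. The two lists compared.** Items 1 to 15 of the short list each have a counterpart in the main list (main items 1–5, 9, 11–15, 17, 18, 21 and 22). The seven main items left out (6, 7, 8, 10, 16, 19, 20) concern sedation, beta-blocker or nitroglycerin, contrast, antibiotic prophylaxis for procedures, previous endoscopy and radiation. That fits the stated reason for shortening. Item 16, PrEP, is the only short-list item with no counterpart in the longer list, and the reason given for shortening does not explain it.

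**4. Does anything else close the gap?**

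- Main item 13 names one antiretroviral combination, ritonavir-boosted lopinavir, and no other.
- Main item 5 (immunomodulatory agents) does not name PrEP or antiretrovirals.
- Main item 11 turns on conditions that compromise ability to take part.
- Antiretroviral history is taken at Visit 1 (both schedules) and at Visit A, but it is not an eligibility criterion for controls.
- The adjustment set under Multivariate modeling does not name PrEP.

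None of these excludes a control on PrEP.

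**5. How many users might there be?** The documents give no prevalence. As an assumption only, take 5% to 20% of otherwise eligible controls.

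- Expected among the 25: 25 × 0.05 = 1.25 to 25 × 0.20 = 5.
- Chance of at least one among the 25: 1 − 0.95^25 = 72% to 1 − 0.80^25 = 99.6%.
- Chance of at least one among the 10 with colonoscopy: 1 − 0.95^10 = 40% to 1 − 0.80^10 = 89%.

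Recruitment through infectious disease clinics, HIV community centers and infectious disease providers (Overview of the Approach) makes some users plausible. It does not fix the rate.

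**6. Where controls enter the analysis.** The Aim 1A sample-size paragraph gives detectable correlations of 0.58 within the uninfected and 0.29 in infected and uninfected subjects together. These depend on the numbers of subjects, which the criterion does not change.

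**The case against.** The strongest case against giving this weight has four parts.

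- **The randomized trial does not depend on it.** Only HIV-positive participants are randomized, the primary analysis compares change in TBR between teduglutide and placebo, and its power calculation uses no controls. The RNA-Seq subset is also HIV-positive only. This stands in full. A reader might infer that the trial's main result is at risk; the documents do not support that.
- **The SAP sets out no formal HIV-versus-control test.** Its univariate work is described in HIV-infected patients, and its two-group tests split by atherosclerosis and by elevated TBR. This largely stands. Controls do enter through the within-uninfected and pooled correlations, and the protocol says that they can serve as a comparison group. The issue is therefore narrow but not empty.
- **No bias is shown.** A reader might infer that PrEP in controls distorts the gut, immune or imaging measures. Nothing in the documents says that PrEP changes permeability, LPS, sCD14, TBR or cognition, and the Background attributes barrier damage to HIV itself. Item 16 suggests that the investigators preferred PrEP-free controls. It says nothing about the size or direction of an effect, nor that any user enrolled.
- **The information to deal with it is partly collected.** Antiretroviral history is already part of the medical history, so users could largely be identified afterwards. This stands, with the reservation that PrEP is not named and may not be reported unless asked about.

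A reader might also take the imaged controls to be only the 10 in Part 2. The neurological visits show that there are 25.

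**Conclusion.** The inconsistency is real and rests on the text alone: one criterion, present in the short list, absent from the long list, and not replaced by anything else. It leaves 25 of 35 controls (71%) without a PrEP exclusion, including all 25 who are imaged, and it splits the 20 parent-study controls 10 and 10 between two rules.

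The consequence is a possible confounding of the judgement whether findings are HIV-specific, not an established bias. The number of users is unknown; the 1 to 5 shown above depends wholly on the assumed 5% to 20%. The randomized comparison and every power figure stand as they are. The comparison of the lists points to an oversight, though the documents do not say so. Priority: minor.

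**What to change.** Reconcile the two exclusion lists so that the same PrEP criterion applies to all 35 HIV-negative controls. One line in the paragraph on criteria for HIV-negative controls would do this.

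For controls already enrolled, use the antiretroviral history taken at Visit 1 and Visit A, ask about PrEP explicitly, and record the answer. Then repeat without users the analyses that include controls: the correlations within uninfected subjects and in pooled subjects, and any HIV-versus-control comparison that is reported. State in the SAP that this is a sensitivity analysis.

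The cost is a one-line amendment, one screening question, slightly narrower control recruitment and one small additional analysis. No sample size changes.

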To achieve these goals, this proposal comprises a multidisciplinary partnership of investigators from endocrinology, infectious diseases, cardiology, radiology, neurology and gastroenterology at Massachusetts General Hospital as well as the immunology laboratories at the Ragon Institute of MGH, MIT and Harvard to investigate the relationship of the gut epithelial integrity and mucosal immunity to atherosclerotic plaque inflammation in HIV patients. Data generated from the studies proposed are expected to address whether the altered gastrointestinal epithelial integrity from HIV infection is closely linked to atherosclerosis via innate immune activation and whether treatment to improve intestinal epithelial integrity can prevent further atherosclerotic disease development and decrease vascular inflammation by curtailing pathologic activation of the innate immune system. Answers to these critical questions will impact the development of novel therapies and preventative strategies for proatherogenic immune activation and CVD in HIV-infected patients.

[figure not shown]
Research Design

To answer Aim 1A, we propose an observational cross-sectional study to investigate the relationships of epithelial integrity (assessed by intestinal biopsy), depletion of GI tract T cells, circulating markers of enterocyte damage (I-FABP³⁸) and microbial translocation (LPS³², sCD14³⁸) to arterial inflammation and coronary artery atherosclerosis and markers of monocyte/macrophage activation. The procedures for the cross-sectional study can be divided into two groups, which we will call **Baseline Study Part 1: Biomarkers, Immunology and Intestinal Permeability Studies** (or simply "Baseline Study Part 1") and **Baseline Study Part 2: Colonoscopy, Cardiac CTA and FD-PET/CT Studies** (or simply "Baseline Study Part 2").

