Medical Record Review: Medical records will be reviewed for relevant clinical data for subjects who are currently followed at MGH or BWH for clinical care. Subjects who receive clinical care from external providers will be asked to sign a Release of Information form. We will request and/or review relevant medical history, laboratory results and treatment history for HIV and/or Hepatitis B and C.

Visit 3 (Colonoscopy)

- 1. Colonoscopy will be performed in the MGH GI endoscopy suite and performed according to standard MGH clinical colonoscopy protocol.
- 2. Blood draw for isolation of cells to be used for immunological studies.

Follow-up Phone call:

The study coordinator or a study investigator will have a follow up phone call with subjects the day after the colonoscopy procedure. The purpose of the call will be to assess how the participant tolerated the procedures and whether an adverse event occurred. If an adverse event occurred, a study physician will speak with the participant. If a study coordinator calls the subject, she/he will inform the subject during the call that a study doctor will call them if they wish.

If eligible, subject will be randomized to either teduglutide or placebo and return for:

Visit 4 (Baseline visit):

- 1. Meet with investigator for dispensing of study drug (including administration of first dose and 30 minute observation)
- 2. Serum HCG will be obtained STAT as a pregnancy test for women prior to FDG-PET
- 3. Blood drawing for RNA-sequencing, and for sera and plasma to be frozen for assays to be run in batch using kits.
- 4. FDG-PET/CT
- 5. Neurocognitive Test Battery administered between 18F-FDG tracer injection and prior to FDG PET/CT scan.
- 6. Center for Epidemiological Studies-Depression Scale (CES-D).
- 7. Cognitive Function Instrument (CFI), and Patient's Assessment of Own Functioning Inventory (PAOFI) Questionnaire.

Visit 4 may be conducted before Visit 3, depending on scheduling availability.

Follow up safety visit 1 month after randomization and then at month 3:

- 1. Blood draw for safety labs, comprehensive metabolic panel, amylase, lipase, CBC with differential, and blood samples will also be stored for biomarkers to be run in batch (sCD14, LPS, I-FABP, sCD163)
- 2. Assess for side effects
- 3. Assess for change in medical problems or medications
- 4. Urine HCG for women
- 5. PAOFI and CES-D at month 3

Final visits at month 6:

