f. Executive function: Trail making test-part B; Victoria Stroop Test Interference These tests have been previously proven to be sensitive to neurocognitive disturbances in HIV infection⁵⁷ and have standardized norms. The complete neurocognitive assessment is designed to last <1 hour, and will be performed at visit 4 in all subjects and also repeated at the final 6 month visit following completion of the interventional study. We will determine the z-score for each test using normative data, average z-scores from all tests, and create a composite cognitive deficit score for subjects at each timepoint. The data will be scored per tests' instructions, and scores will be entered into REDCap database.

Remuneration

Transportation to and from visits will also be additionally subsidized and a meal ticket as well as parking will be provided at each visit.

Participants who participate in only Baseline Study Part 1 (2-visit cross-sectional substudy) will receive \$75.

Participants who undergo Baseline Study Part 1 and Part 2, (4-visit cross-sectional substudy including colonoscopy, cardiac CTA and FDG-PET) will receive \$375.

Participants in the interventional Randomized Study of Teduglutide vs. Placebo study will receive up to \$825 for completion of study.

HIV-negative control participants who undergo testing for neurological substudy (2-visits cross-sectional substudy including cardiac CTA and FDG-PET) will receive \$125.

Pro-rated remuneration

- In addition to providing parking and assistance with transportation when needed, participants will receive up to \$825 for the Randomized Study of Teduglutide vs. Placebo:
- \$50 after the completion of screen visit 1
- \$25 after the completion of screen visit 2 (bionutrition).
- \$225 after completion of screen visit 3 (colonoscopy)
- \$75 after the completion of the baseline visit
- \$25 after each safety visit (1, 3 month)
- \$400 at the completion of the final study visits

Participants in the cross-sectional study will receive up to \$375:

• \$50 after the completion of screen visit 1

- \$25 after the completion of screen visit 2 (bionutrition)
- \$225 after completion of screen visit 3 (colonoscopy)
- \$75 after the completion of visit 4

Participants in the neurological substudy will receive up to \$125:

- \$50 after the completion of visit A
- \$75 after the completion of visit B

Costs

There will be no cost to the subject for participation in the study.

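### The visit-order sentence lets Visit 4, which includes the first dose, precede the Visit 3 colonoscopy, and nothing exempts randomised participants

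*Combined protocol and SAP*

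**What the plan says.** Section V (Study Procedures) sets out four baseline visits. Visit 3 is the colonoscopy with biopsies. The text that follows it reads "If eligible, subject will be randomized to either teduglutide or placebo and return for" Visit 4, the baseline visit. The first item of Visit 4 is "Meet with investigator for dispensing of study drug (including administration of first dose and 30 minute observation"). The same visit holds the FDG-PET/CT, blood draws, neurocognitive battery and questionnaires. The Visit 4 list is followed by "Visit 4 may be conducted before Visit 3, depending on scheduling availability". Scheduling is the only condition given.

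Other parts of the protocol place the colonoscopy before the trial. Section II (Research Design) names the second baseline block "Baseline Study Part 2: Colonoscopy, Cardiac CTA and FD-PET/CT Studies". Section III (Overview of the Approach) says "The 60 HIV-positive patients who complete Baseline Studies Part 1 and Part 2 will enter the" randomised study, and that the Part 1 and Part 2 tests "will serve as the baseline measurements for the randomized study (they are not repeated"). Section VII (Teduglutide) relies on the screening colonoscopy to find undiagnosed colon cancer and keep those participants out of the interventional study. Section V (Colonoscopy) provides for removing polyps found before study medication starts or at the end of treatment.

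**The concern.** Staff who follow the swap sentence as written could dose a participant at Visit 4 and perform the baseline colonoscopy afterwards. Two things would be at stake.

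**Safety.** Section I describes GLP-2 as a trophic factor for the intestine, and Section VII reproduces the label's polyp and adenoma cases. The screening colonoscopy is part of the protocol's response to that risk. After a swap, the search for cancer and polyps would come once the participant had started the analog or placebo. A cancer found then would be a discontinuation of a treated participant under Section IX, not a screening exclusion.

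**Data.** Biopsy tissue, mucosal cells and ileal luminal fluid come only from the colonoscopy. Taken after a teduglutide dose, they are not pre-treatment baselines for the epithelial-integrity effects in Aim 2. Nor are they untreated samples for the cross-sectional Aim 1A, which uses the same participants.

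**Working it through.** The plan gives no figure on this point, so the check sets the relevant texts side by side and counts who is affected.

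1. **Who has both visits.** On the planned numbers in Section III, Part 2 is done by 60 HIV-positive patients and 10 HIV-negative controls: 60 + 10 = 70. All 60 HIV-positive patients are due to enter the trial, and Section IV keeps controls out of it. So 60/70 = 85.7% of those to whom the swap sentence could apply at baseline are trial participants. It cannot be read as mainly about people who take no drug.

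2. **What the swap moves.** The sentence moves Visit 4 as a whole. Visit 4 item 1 is dispensing and first dose. No sentence separates the drug from the assessments.

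3. **Whether other text restores the order.** Visit 2 item 5 says that drug does not start until Visit 4 is over. This ties drug to Visit 4, not to Visit 3, so it gives no protection once the visits are swapped. It also fits poorly with a first dose given during Visit 4, unless it means home injection after a supervised first dose.

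4. **What the rest of the protocol presupposes.**
   - Section III: Part 2, which includes the colonoscopy, is completed before trial entry.
   - Section V: randomisation depends on eligibility and is placed after Visit 3.
   - Section VII: the colonoscopy excludes undiagnosed colon cancer from the interventional study, which works as an entry check only if it comes before drug.
   - Section V, Colonoscopy: the polyp sentence assumes that the first colonoscopy precedes study medication.
   - Remuneration: payment "after completion of screen visit 3 (colonoscopy") is listed apart from payment "after the completion of the baseline visit". This is weak support, because the colonoscopy carries the same screening label for cross-sectional participants.

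5. **Length of exposure.** No maximum interval between Visits 3 and 4 is stated. Section IV sets 0.025 mg/kg/day for the first week and 0.05 mg/kg/day after that if tolerated. A short swap would mean half-dose exposure before colonoscopy; a longer one could mean full dose. The text sets no upper limit.

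6. **Which measurements are affected.** Three sample types are obtained only at colonoscopy: biopsies, mucosal cells and luminal fluid. The Visit 3 immunology blood would also be post-dose, but Visits 1 and 2 supply earlier blood, and the sugar-probe test is at Visit 2. The primary endpoint, TBR by FDG-PET, is measured at Visit 4. Moving that visit relative to Visit 3 leaves the scan and the first dose in the same visit.

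7. **Size.** With 30 planned per group, between 0 and 30 teduglutide participants could have drug-exposed baseline tissue. The documents give neither a swap rate nor an early mucosal effect, so nothing narrower can be derived.

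**The case against.** The strongest reply is that the text is ambiguous rather than contradictory. One reading fits every section: the Visit 4 assessments may move while randomisation and drug wait for the colonoscopy. Drug cannot be dispensed without randomisation, randomisation requires eligibility, and the swap sentence does not claim to waive either. It also has harmless uses, for the 10 controls and for the month-6 repeat visits. This reading is probably what was meant, and it stands as the likely intent. But it is an unstated exception to an explicit permission, and a safety check should not depend on staff inferring it.

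The protocol also has safeguards that do not depend on visit order. Section III excludes clinically significant gastrointestinal disease, including colon cancer, a first-degree relative with colon cancer, and most malignancy within 5 years. Sections V and VII add an end-of-study colonoscopy and a fecal immunochemical test at 1 year. This stands too, and limits the residual safety risk to undiagnosed lesions.

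A reader might infer that the polyp sentence forbids, or leaves uncovered, removal at a colonoscopy done after dosing. It does not go that far. It describes when study colonoscopies are expected and is evidence of the intended order, not a restriction.

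Figures 1a and 2, and the text between the Costs paragraph and the statistical section, could not be checked. They may state the order.

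**Conclusion.** The point holds as a wording conflict that should be fixed. Read literally, the swap sentence permits dosing before the colonoscopy that is meant to screen for cancer and polyps and to supply baseline tissue. Nothing in the text that could be checked prevents it.

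Its reach is up to 60 randomised participants for the safety check and up to 30 for drug-exposed tissue. If no visits were swapped, the data effect is zero and only the wording needs repair. If some were, and if teduglutide already acts on the mucosa by then, the measured tissue change in Aim 2 would tend to be too small. The documents quantify neither condition.

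Two stronger conclusions are tempting but unsupported. A reader might infer that participants were dosed before colonoscopy; the documents describe what is allowed and record no such case. A reader might also infer that the primary result is compromised; the swap does not materially affect the TBR endpoint, its power or the sample size.

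**What to change.** Amend the sentence under Visit 4 to say that its imaging, blood draws and questionnaires may precede Visit 3. Randomisation, dispensing and the first dose should occur only after the Visit 3 colonoscopy has been completed and reviewed and the Visit 4 baseline assessments are done. Align Visit 2 item 5 and Visit 4 item 1 with this, so that the supervised first dose and the start of home injection are clearly distinguished.

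If any participant was dosed before Visit 3, flag that participant's biopsy, mucosal-cell and luminal-fluid samples, and run the Aim 1A and Aim 2 tissue analyses with and without them. Outright exclusion is not needed, since placebo participants' samples would still be free of drug.

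The cost is a short protocol amendment, slightly less scheduling flexibility and, when visits are swapped, possibly a separate dosing contact with the 30-minute observation. The primary analysis and sample size stay as they are.
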